**II. TITLE:**

Examining the Impact of Sirolimus on Ketamine's Antidepressant Effects

**III. PURPOSE:**

Ketamine is an anesthetic agent, recently found to exert a rapid and potent antidepressant effect in severely depressed patients. Controversy exists in the field regarding how ketamine works in the brain and thus what underlies its rapid and profound antidepressant effects. A better understanding of the mechanism of the neuropsychiatric effects of ketamine are critically important, as pharmacological modulation of these effects can assist in the development of novel medications for the treatment of multiple psychiatric disorders including depression and schizophrenia.

The aim of the study is to provide insight into the impact of the immunosuppressant drug sirolimus (also known as rapamycin; known to have impact on depressive symptoms from molecular and preclinical studies), on the antidepressant effects of the prototypal rapid-acting antidepressant medication, ketamine. More specifically, the study will examine whether sirolimus shows significant interactive effects (i.e., synergy or antagonism) with ketamine in participants with treatment resistant depression as measured by the use of the clinician-administered Montgomery Asberg Depression Rating Scale (MADRS). We will also test the tolerability of the combined ketamine and sirolimus treatment. Secondary outcome measures are designed to measure the effects of sirolimus on the tolerability of ketamine.

- **Aim 1:** To characterize the effects of a single dose of sirolimus prior to a low dose of ketamine in subjects with antidepressant-resistant depressive symptoms.  
**Design:** 30 participants will be randomized into one of two groups at Time/Infusion 1 — ketamine+sirolimus (with placebo at Time 2) or ketamine+placebo (with sirolimus dose at Time 2).  
**Hypothesis:** Sirolimus will interact with ketamine by attenuating or potentiating the antidepressant effects.
- **Aim 2:** To examine the safety and tolerability of combined ketamine-sirolimus treatment.  
**Design:** The Systematic Assessment for Treatment Emergent Effects (SAFTEE) scale will be completed during each visit to compare the adverse events profile in the sirolimus and the placebo groups.

**Hypothesis:** Participants will tolerate the combined treatment with no residual adverse effects.

- **Aim 3:** To identify biological markers of the combined ketamine-sirolimus treatment.
- **Design:** Inflammatory biomarkers will be measured in 18 depressed participants who will receive open-label sirolimus+ketamine.
- **Hypothesis:** Twenty-four hours post-treatment, sirolimus+ketamine will significantly reduce the inflammatory biomarkers.

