**A. Phase Two Research Procedures (following DSMC approval) Subjects:**

We anticipate recruiting and screening approximately 75 male and female Veterans and non-Veterans/civilians, between the ages of 21-65 years, in order to meet our target enrollment goals. In order to account for subject dropouts and the potential need to discontinue subjects before study completion (see below for discontinuation criteria) and retain a sample of 30 subjects completing the double-blind treatment phase, 45 eligible subjects who meet criteria for Major Depressive Episode as determined by the Mini International Neuropsychiatric Interview (MINI) the study inclusion criteria outlines below, will be randomized into the study. Note, this study will not include a healthy control group as we are interested specifically in the antidepressant effects of ketamine and sirolimus and therefore require subjects with current depression.

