***Data Analysis:***

This study, investigating the impact of sirolimus on ketamine's rapid antidepressant effects, is the first of its kind. In order to assess study utility and to determine if medication dose adjustments may be useful, we plan to do interim analyses after completion of the first 6 subjects, with subjects randomized according to block randomization (block of six). We propose to study 30 patients, overall. This sample size is feasible within the funding available for this project and will provide 80% power for detecting ketamine-sirolimus interaction effects of moderate size ( $d'=.53$ ), assuming a two-tailed alpha=.05. The data analysis plan is provided only for the primary outcome variable, the MADRS score. The normality of the data will be tested initially using probability plots and the Kolmogorov-Smirnov tests. These data are frequently skewed and so we plan to analyze them using a non-parametric approach to repeated measures data. The data will be first ranked and then fitted with a mixed-effects model with an unstructured variance-covariance matrix and p values adjusted for ANOVA-type statistics. In these models sirolimus (active vs. placebo) and time will be fitted as within subjects variables. All interactions will be fitted. Age and sex will be treated as covariates/grouping factors. Post-hoc analyses will be conducted to interpret interactive effects significant at the p=0.05 level. Subject will be used as the clustering variable. Plasma ketamine and ketamine metabolite levels will be analyzed using linear mixed models. All secondary measures will be assessed using similar methodology. Behavioral measures of Phase 3 will use similar methodology. The collection, processing and analysis of peripheral inflammatory biomarkers will be completed under a separate protocol and consent (i.e., CA0008).

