***Sirolimus Administration:***

Sirolimus is a commonly prescribed immunosuppressant (maximum daily dose is 40 mg); FDA approved for prophylaxis of renal transplant rejection. The limited administration and low dose proposed in this study was selected to yield efficacy but minimize side effects. Short-term administration (i.e., a single 6 mg dose) is anticipated to have limited, if any, side effects. Potential side effects include nausea, vomiting, diarrhea, constipation, stomach pain, headache, skin rash, and joint pain. Other adverse reactions related to treatment with sirolimus include: peripheral edema, hypertriglyceridemia, hypertension, hypercholesterolemia, increased creatinine, fever, urinary tract infection, anemia, pain, thrombocytopenia, susceptibility to infection, lymphoma, and malignancy, hypersensitivity reactions, exfoliative dermatitis, angioedema, fluid accumulation and wound healing, proteinuria, interstitial lung disease, and increased risk of calcineurin inhibitor-induced hemolytic uremic syndrome/thrombotic thrombocytopenic purpura/thrombotic microangiopathy (HUS/TTP/TMA).

Also uncommon, but possible, is an allergic reaction to sirolimus. Signs of such a reaction include the acute onset of hives, difficulty breathing, swelling of the face lips, tongue, or throat. As described above, a trained physician and nurse will be in attendance throughout the drug administration and infusion to monitor subjects for any side effects or other adverse events.

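### Aim 2 hypothesises no residual adverse effects, but its only analysis route is a comparison for difference with no margin, acceptable rate or interval, so the hypothesis cannot be established

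*Combined protocol and SAP*

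**What the plan says.** Aim 2 (III. Purpose) has two parts. The hypothesis is that "Participants will tolerate the combined treatment with no residual adverse effects". The design is to complete the SAFTEE at each visit "to compare the adverse events profile in the sirolimus and the placebo groups". The same section makes tolerability the secondary outcome: "Secondary outcome measures are designed to measure the effects of sirolimus on the tolerability of ketamine".

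The Data Analysis section limits its own scope: "The data analysis plan is provided only for the primary outcome variable, the MADRS score". For MADRS it says "The data will be first ranked and then fitted with a mixed-effects model with an unstructured variance-covariance matrix", with ANOVA-type statistics. For everything else it says "All secondary measures will be assessed using similar methodology".

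The power statement in that section (30 patients, 80% power, d' = 0.53, two-tailed alpha 0.05) concerns the ketamine-sirolimus interaction. The Phase Two Subjects section explains the numbers: to "retain a sample of 30 subjects completing the double-blind treatment phase, 45 eligible subjects who meet" the inclusion criteria are to be randomised.

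Neither section defines a residual effect, sets an acceptable event rate or margin, asks for a confidence interval, or names a test for event proportions.

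**The concern.** The hypothesis states an absence, while the method can only reject an absence. A significant difference would count against Aim 2. A non-significant one would leave it undecided, because a small trial can miss a sizeable excess. No result of the stated analysis can support the hypothesis as worded.

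What is at stake is the sentence in the final report that answers Aim 2. Without a margin or an interval, nothing in the plan stops a non-significant SAFTEE comparison from being reported as tolerability, and nothing tells the reader which event rates the data have ruled out.

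There is also a limit on what the comparison can see. SAFTEE is described as a self-report instrument. The risk section lists sirolimus reactions that include "peripheral edema, hypertriglyceridemia, hypertension, hypercholesterolemia, increased creatinine, fever, urinary tract infection, anemia". Some of these, such as raised lipids or creatinine and anemia, are laboratory findings. Routine bloods appear under the screening assessments, with further tests only when clinically indicated, and the blood draws described for infusion visits are for drug levels.

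**Working it through.** **Inputs.** From the protocol: 30 completers and 45 randomised (Phase Two Subjects); a crossover in which each patient receives ketamine once with sirolimus and once with placebo (Ketamine Administration); two-tailed alpha 0.05, 80% power and d' = 0.53 (Data Analysis). Assumed: the event counts below, because the protocol gives none, and that SAFTEE items are analysed as event present or absent, because the protocol does not say how they are scored.

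**Step 1. The plan's own figure.** Paired t-test, n = 30, d = 0.53: noncentrality 0.53 × √30 = 2.903, critical t on 29 df = 2.045, power = 80.1%. The stated 80% is reproduced as a within-patient comparison. It says nothing about adverse events.

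**Step 2. What a difference test does with a real excess.** Let b be the number of patients with the event only under sirolimus and c the number only under placebo, out of n = 30. Some placebo-only events are to be expected: every patient also receives ketamine with placebo, and the risk section lists nausea and vomiting for both drugs.

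- Exact McNemar: p = 2 × P(X ≥ b), X binomial(b + c, 0.5).
- Mid-p: the exact p minus P(X = b).
- Uncorrected McNemar: (b − c)²/(b + c) on 1 df.
- Paired t: mean (b − c)/30, SE = √{[(b + c) − (b − c)²/30]/(29 × 30)}. Ranking a 0/1 outcome only rescales it, so this is a simple stand-in for the planned ranked within-subject model. The full model with time, age and sex cannot be run without data.

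For 6 vs 1:
- Exact: 2 × (7 + 1)/128 = 0.125.
- Mid-p: 0.125 − 7/128 = 0.070.
- Uncorrected: 25/7 = 3.57, p = 0.059.
- Paired t: SE = √(6.167/870) = 0.0842, t = 0.1667/0.0842 = 1.98, p = 0.057.

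| b vs c | Net excess | Exact | Mid-p | Uncorrected | Paired t | 95% CI from paired t |
|---|---|---|---|---|---|---|
| 5 vs 0 | 16.7 points | 0.0625 | 0.031 | 0.025 | 0.023 | not needed |
| 6 vs 1 | 16.7 points | 0.125 | 0.070 | 0.059 | 0.057 | −0.6 to 33.9 |
| 7 vs 2 | 16.7 points | 0.180 | 0.109 | 0.096 | 0.096 | −3.1 to 36.5 |
| 8 vs 2 | 20.0 points | 0.109 | 0.065 | 0.058 | 0.056 | −0.6 to 40.6 |

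The intervals are the mean ± 2.045 × SE; for 6 vs 1, 16.7 ± 2.045 × 8.42. The 6 vs 1 and 8 vs 2 cases lie close to 0.05. A Wald z-test, with SE = √[(b + c) − (b − c)²/30]/30, gives z = 0.1667/0.0828 = 2.01 for 6 vs 1 and would cross the line. For 7 vs 2 it gives 0.1667/0.0953 = 1.75 and does not. In each of the last three rows, an excess of 17 to 20 points can fail to reach significance while the interval reaches 34 to 41 points.

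**Step 3. The best possible result.** With zero events in n patients, the two-sided 95% upper limit is 1 − 0.025^(1/n).

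- n = 30: 11.6% (one-sided 95%: 1 − 0.05^(1/30) = 9.5%).
- n = 45: 7.9% (one-sided: 6.4%).

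The number exposed to sirolimus should lie between these, since a patient given placebo first who leaves before Infusion 2 never receives it. Even a clean record cannot show that there are no adverse effects.

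**The case against.** **The result depends on the test.** The protocol names no test for event proportions, and exact McNemar appears nowhere in it. A reader might infer that an event seen only with sirolimus in 5 of 30 patients would be missed. The documents do not support that as a fact: the exact test gives 0.0625, but the stand-in closest to the stated method gives 0.023. Power figures tied to the exact test are likewise not properties of this plan. This stands, and it is why the argument rests on counts with some placebo-only events and on the zero-event limits.

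**No decision rule is written.** A reader might infer that the sponsor will take non-significance as proof of tolerability. The protocol says only that profiles will be compared. This stands too. The finding is that the plan leaves the reading open.

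**Residual has a meaning.** The protocol uses the word for effects asked about at the 24-hour visit, the 28-day call and the other follow-ups. On a plain reading, even one such event attributed to the treatment would contradict the hypothesis, whatever the p-value. That is fair, and it means residual events need their own line in the analysis.

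**Safety does not rest on one comparison.** Events are attributed and graded, the principal investigator reviews them after every subject, and an independent committee reviews safety twice yearly. This protects participants during the trial, but it does not say how Aim 2 will be concluded.

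**Some listed reactions can be seen.** Edema, fever, hypertension and urinary infection may show as symptoms or signs, and Table 2 schedules vital signs and urinalysis at both infusions. So only the laboratory effects escape. The portion of Table 2 available to this review begins at the MADRS row, so the absence of post-dose safety bloods is read from the visit descriptions and the Medical Assessments section.

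**Phase Three.** Its remark that returning participants tolerated the drug concerns each person's own exposure. It is not a group claim drawn from a null test and adds nothing here.

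**Conclusion.** The concern holds in this limited form: Aim 2 states an absence, and the only route offered to it is a test of difference with no margin, acceptable rate or interval, in a trial sized for efficacy. A net excess of 17 to 20 points can be non-significant under the four paired tests tabulated, with p from about 0.056 to 0.180 across the three examples. Zero events would leave rates up to 11.6% (30 patients) or 7.9% (45 patients) unexcluded.

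This rests on assumed event counts, on treating SAFTEE items as present or absent, and on a simplified stand-in for the ranked model. The zero-event limits need none of the assumed counts and no choice of difference test; they are the firmest part. The documents do not support the stronger claims that a given count would be missed, or that the trial will declare tolerability from a non-significant result. The point concerns a secondary aim and leaves the MADRS analysis untouched.

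**What to change.** Restate Aim 2 as estimation and drop the absence of residual effects as a hypothesis to confirm. Specifically:

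1. For each SAFTEE event, for any event, and for events still present at the follow-up visits (with residual defined by named visits), report the within-patient risk difference, sirolimus minus placebo, with a 95% confidence interval from a named paired method.
2. Give the upper limit as the excess that has been excluded, and state that a non-significant difference will not be read as tolerability.
3. State the denominators: patients with both infusions for the paired difference, and everyone who received sirolimus for the simple event rates.
4. Limit the SAFTEE-based claim to reported symptoms, since no post-dose safety bloods are described. Estimation does not close that gap; the narrower claim acknowledges it.

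The cost is a change to the objective and analysis wording and one extra table, with no new patients or procedures. The safety claim becomes more modest.

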#### IV. BACKGROUND

Despite 50 years of scientific progress, major depression remains among the leading causes of distress and disability in the world with a 21-fold increase in suicide attempts during major depressive episodes. In the United States, the estimated lifetime prevalence is approximately seventeen percent. One potential reason for this sad state of affairs is that depression is treated today in basically the same way as it was in the early 1960's, when the prescription of tricyclic antidepressants became widespread. Depression is treated predominately by medications that enhance the impact of two brain chemical messengers (serotonin, norepinephrine). While more than 20 antidepressant medications are currently available, the efficacy of these medications is limited. These antidepressants only produce clinical remission in approximately 30% of patients in their initial clinical trial, after two drugs are tried, each new attempt at treatment only 10%-15% of patients would remit, and after multiple trials over a year only 60%-70% of patients would have a satisfactory response to treatment. Further, among those patients who do respond, clinical response only emerges, on average, after 7 weeks of treatment. From these data, it is evident that there is tremendous societal need for a novel class of antidepressants that can offer (1) rapid acting effects and (2) efficacy in patients not achieving adequate benefit from existing medications. Over the last decade, accumulating evidence has shown that low dose of ketamine, a *N*-methyl-D-aspartate (NMDA) receptor antagonist, may possess both of these properties.

Members of our research group produced the first hint of a new approach that might address some of the limitations of existing antidepressant treatments. We have studied ketamine, a drug that acts on brain systems that use glutamate as a chemical messenger and noted a very interesting clinical report from the late 1950s and later basic animal research studies that suggested that drugs that blocked elements of glutamate signaling in the brain might have antidepressant effects. In 2000, we published a report suggesting that ketamine might have remarkable antidepressant effects. First, rather than taking 7 weeks to respond, patients began to respond to treatment as early as within several hours of the first dose of ketamine. Second, rather than producing response in 10%-15% of patients "treatment-resistant" depression symptoms, 50% of patients met response criteria within 24 hours of their first ketamine. Subsequent studies by other groups using ketamine and other ketamine-like drugs essentially replicated these observations in patients with unipolar and bipolar (manic-depressive) depression. Other groups, for example, showed that suicidal thoughts or feelings that had failed to respond to other medication and psychotherapy treatments responded rapidly to ketamine. In addition, ketamine worked even in patients who failed to respond to electroconvulsive therapy. Most importantly, the antidepressant effects of ketamine appear to be sustained by repeated ketamine administration. To date, more than 15 studies have investigated the efficacy of 0.5 mg/kg ketamine infusion in more than 300 depressed

patients. These studies consistently showed a rapid antidepressant action within 4-hours of ketamine's administration, with a short-term response rate ranging from 43% to 90%.

The mechanisms of action and underlying neurobiology of ketamine's antidepressant effects are not yet fully known or understood. We believe that advancing our understanding of how ketamine acts on the brain to produce its antidepressant effects is critical for improving the effectiveness and safety of ketamine and/or novel drugs development from the ketamine model. The safety concerns related to ketamine emerge from its abuse liability and its propensity to produce transient changes in cardiorespiratory function as well as perception and mentation in humans. In order to limit the risks of ketamine or to engineer a better ketamine, we need to better understand how it works.

There is controversy in the field regarding how ketamine produces its antidepressant effects. Specifically, investigators argue whether the rapid-antidepressant effects of the drug are secondary to direct action or indirect consequence of ketamine's effects on brain networks. Stress and depression appear to strip the brain of fine connections between nerve cells (dendritic spines) within brain circuits that regulate mood. Ketamine appears to cause these fine connections to regrow rapidly in animals for a period that lasts as long as the antidepressant effects of a single ketamine injection last in humans, i.e., up to a few weeks.

The indirect network effects of ketamine, sometimes described as "stimulating the go pathway" described in figure 1, is central to our proposal. One line of research suggests that the ability of ketamine to stimulate glutamate release and to thereby activate a signaling pathway in nerve cells involving a protein called "the mammalian target of rapamycin" (mTOR). According to this theory, the co-administration of sirolimus, an immunosuppressant drug commonly prescribed for prophylaxis of renal transplant rejection, should **reduce** the antidepressant effectiveness of ketamine.

However, the other major hypothesis is related to the ability of ketamine to directly block signaling via the "stop pathway", i.e., to remove an inhibition on dendritic spine growth. By blocking a very specific subtype of receptor target for glutamate in the brain (NR2B subunit-containing NMDA glutamate receptor), ketamine may directly help dendritic spines to regrow in a manner that is independent of mTOR. Sirolimus has been repeatedly shown to have the potential

[figure not shown]

Figure 1. The top figure illustrates the presence of synaptic (receives directly released glutamate) and extrasynaptic (receives glutamate "spillover" from the synapse) glutamate receptors. Ketamine may exert its treatment effects either indirectly by increasing glutamate release and stimulating the "go pathway" (synaptic AMPA glutamate receptors) or by blocking the "stop pathway" (extrasynaptic NR2B-containing NMDA glutamate receptors).

to produce anti-depressant effects in animals and to have beneficial effects in animal models of other neuropsychiatric disorders, perhaps by having anti-inflammatory effects in the brain. A study suggests that standard antidepressant administration reduces mTOR levels, an effect that would mimic the acute effects of sirolimus. Thus, if the direct effects of ketamine on the “stop pathway” pertain, then the antidepressant effects of sirolimus might *increase* the efficacy of ketamine.

[figure not shown]
Molecular studies in animals have found that synaptic deficits are precipitated by reduction in neurotrophins such as BDNF, and by inhibition of mTOR signaling pathway. Inhibition of mTOR signaling or reduction of BDNF leads to depressive-like behavior and blocks the effect of antidepressants in animal models of depression. Enhancing mTOR signaling or increasing BDNF produces antidepressant effects in preclinical studies. In humans, reduced central and peripheral BDNF levels were found in depressed patients and a functional variant of BDNF polymorphism (Val66Met) has been related to depression, especially in males. Together these data posit that enhancing BDNF and mTOR signaling leading to prefrontal synaptic formation (synaptogenesis), and reversal of stress/depression-induced neuronal atrophy and synaptic dysconnectivity is a required step for efficacious antidepressant treatment. Traditional antidepressants, targeting the monoaminergic system, were found to increase BDNF and synaptogenesis. However, these effects were only evident following chronic treatment, which is in line with the delayed antidepressant response to these drugs in humans. Therefore, it is proposed that rapid acting antidepressants would need to directly target the induction of mTOR signaling, the increase of BDNF levels, and the ultimate enhancement of prefrontal synaptogenesis.

Thus, we have the basis for proposing to test the interactive effects of ketamine and sirolimus, a simple clinical trial that has: 1) the potential to shed fundamental light on how ketamine produces rapid clinical improvement and 2) to suggest a strategy for increasing the effectiveness of ketamine. If sirolimus reduces the antidepressant effects of ketamine, then we will know that stimulation of mTOR is critical to the antidepressant effects of ketamine, leading us to test other drugs that directly stimulate this signaling pathway.

The results of Phase 1 & 2 of this study have shown sirolimus pretreatment significantly prolong the antidepressant effects of ketamine and triples the antidepressant response rate at 2 weeks following treatment (see Fig. 2). Given the role of the immune system in the pathology and treatment of depression, it was proposed that the anti-inflammatory effects of the combined treatment of sirolimus+ketamine underlie the robust enhancement in treatment response rate. Therefore, we will conduct a pilot study to determine the effects of sirolimus+ketamine on a range of inflammatory biomarkers implicated in the pathology of depression. The aim of this Phase 3 of the study is to provide preliminary data about target engagement of the sirolimus+ketamine treatment. The treatment and follow-ups will be comparable to the Phase 2 study, but only open-label sirolimus+ketamine will be administered and the weekly follow-ups will be extended to 4 weeks post-treatment.

